Current treatment approach for high-risk patients include induction chemotherapy (reduce tumor burden by shrinking tumor), local control (delayed surgery to remove tumor), consolidation (myeloablative therapy with stem cell rescue performed in tandem) and maintenance therapy (GD2-directed therapy, which is painful and toxic).¹¹ A published meta-analysis of three European SIOP Neuroblastoma Group (SIOPEN) trials on standard backbone chemotherapy regimens showed poor outcomes in both relapsed and refractory neuroblastoma patients.¹² It is important to note that, unlike childhood leukemias, there is no standard approach for high-risk neuroblastoma patients who suffer a relapse and there is no known curative therapy. Response rates in clinical trials of relapsed/refractory neuroblastoma ranged from 20-64%.¹² After treatment, progression occurred in 54% of patients with refractory disease versus 87% of patients with relapsed disease.¹² Overall median OS was 16.1 months, with longer median OS for patients with refractory disease compared to relapsed disease.¹² Neuroblastoma has significant heterogeneity, therefore risk stratification has become an important factor in identifying novel biomarkers to inform treatment decisions.⁹

Initial reports of anaplastic lymphoma kinase (ALK) gene amplification and overexpression suggested a role of ALK in neuroblastoma.^{13,14} Notably, ALK activating mutations were first discovered in the germline of families where the disease is inherited, and subsequently found to be present in somatic tissue in ~10% of patients at diagnosis.¹⁵⁻¹⁸ The majority of patients with familial neuroblastoma have germline mutations in ALK.¹⁸ Sporadic neuroblastoma tumors also occasionally harbor ALK abnormalities, including 4% of tumors with genomic amplification and approximately 10% with missense mutations.^{14,17-19} Furthermore, the presence of ALK mutation correlates with worse prognosis in high and intermediate risk patients.²⁰ The detection of ALK mutations and/or amplifications in primary neuroblastomas, provides a molecular rational for targeted therapy of neuroblastoma.¹⁶ It has been demonstrated that downregulation of ALK suppressed proliferation of neuroblastoma cells harboring mutated ALK.¹⁵

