8.7.4 Safety endpoints

PFIZER CONFIDENTIAL

All adverse events collected on the DCT will be listed and summarized for all data reporting milestones. Adverse Events will be coded using the latest Medical Dictionary for Regulatory Activities (MedDRA) version. The version used will be indicated in the data summaries and listings.

All patients who discontinue treatment due to safety reasons such as AEs, will be captured and reported as a reason for discontinuation in the patient disposition summaries and listings.

All Adverse Event data captured will be listed. In addition a separate listing will be presented for Serious Adverse Events.

The number and percentage of patients reporting at least one Adverse Event will be summarized within the following categories:

- Adverse Events
- Treatment-related
- Serious
- Serious treatment-related

The following summary tables will also be presented:

- Number and percentage of patients and number of Adverse Events by MedDRA System Organ Class (SOC) and Preferred Term (PT);
- Serious Adverse Events by SOC and PT.

[figure not shown]
SOC and PT will be presented in decreasing frequency of the total number of patients with Adverse Events. If a patient experienced more than one Adverse Event, the patient will be counted once for each SOC and once for each PT.

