10. MANAGEMENT AND REPORTING OF ADVERSE EVENTS/ADVERSE REACTIONS

REQUIREMENTS

The table below summarizes the requirements for recording safety events on the data collection tool and for reporting safety events on the non-interventional study (NIS) adverse event monitoring (AEM) Report Form to Pfizer Safety. These requirements are delineated for three types of events: (1) serious adverse events (SAEs); (2) non-serious AEs (as applicable); and (3) scenarios involving drug exposure, including exposure during pregnancy, exposure during breast feeding, medication error, overdose, misuse, extravasation, lack of efficacy, and occupational exposure. These events are defined in the section “Definitions of safety events.”

PFIZER CONFIDENTIAL

Safety event	Recorded on the data collection tool	Reported on the NIS AEM Report Form to Pfizer Safety within 24 hours of awareness
SAE	All	All
Non-serious AE	All	All
Scenarios involving exposure to a drug under study, including exposure during pregnancy, exposure during breast feeding, medication error, overdose, misuse, extravasation, lack of efficacy, and occupational exposure	All (regardless of whether associated with an AE), except occupational exposure	All (regardless of whether associated with an AE) Note: Any associated AE is reported together with the exposure scenario.

For each AE, the HCP must pursue and obtain information adequate both to determine the outcome of the AE and to assess whether it meets the criteria for classification as a SAE (refer to section "Serious Adverse Events" below).

Safety events listed in the table above must be reported to Pfizer within 24 hours of awareness of the event by the HCP **regardless of whether the event is determined by the HCP to be related to lorlatinib**. In particular, if the SAE is fatal or life-threatening, notification to Pfizer must be made immediately, irrespective of the extent of available event information. This timeframe also applies to additional new (follow-up) information on previously forwarded safety event reports. In the rare situation that the HCP does not become immediately aware of the occurrence of a safety event, the HCP must report the event within 24 hours after learning of it and document the time of his/her first awareness of the events.

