The HCP is required to assess and record the causal relationship. For all AEs, sufficient information should be obtained by the HCP to determine the causality of each AE. For AEs with a causal relationship to lorlatinib, follow-up by the HCP is required until the event and/or its sequelae resolve or stabilize at a level acceptable to the HCP, and Pfizer concurs with that assessment.

An HCP's causality assessment is the determination of whether there exists a reasonable possibility that lorlatinib caused or contributed to an AE. If the HCP's final determination of causality is "unknown" and s/he cannot determine whether lorlatinib caused the event, the safety event must be reported within 24 hours.

[figure not shown]
If the HCP cannot determine the etiology of the event but s/he determines that lorlatinib did not cause the event, this should be clearly documented on the data collection tool and the NIS AEM Report Form.

DEFINITIONS OF SAFETY EVENTS

Adverse events

An AE is any untoward medical occurrence in a patient administered a medicinal product. The event need not necessarily have a causal relationship with the product treatment or usage. Examples of AEs include but are not limited to:

PFIZER CONFIDENTIAL

- Abnormal test findings (see below for circumstances in which an abnormal test finding constitutes an AE);
- Clinically significant signs and symptoms;
- Changes in physical examination findings;
- Hypersensitivity;
- Lack of efficacy;
- Drug abuse;
- Drug dependency.

Additionally, for medicinal products, they may include the signs or symptoms resulting from:

- Drug overdose;
- Drug withdrawal;
- Drug misuse;
- Off-label use;
- Drug interactions;
- Extravasation;
- Exposure during pregnancy;
- Exposure during breast feeding;
- Medication error;
- Occupational exposure.

Abnormal test findings

The criteria for determining whether an abnormal objective test finding should be reported as an AE are as follows:

- Test result is associated with accompanying symptoms, and/or
- Test result requires additional diagnostic testing or medical/surgical intervention, and/or

PFIZER CONFIDENTIAL

- Test result leads to a change in study dosing or discontinuation from the study, significant additional concomitant drug treatment, or other therapy, and/or
- Test result is considered to be an AE by the HCP or sponsor.

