Merely repeating an abnormal test, in the absence of any of the above conditions, does not constitute an AE. Any abnormal test result that is determined to be an error does not require reporting as an AE.

Serious adverse events

A SAE is any untoward medical occurrence in a patient administered a medicinal or nutritional product (including pediatric formulas) at any dose that:

- Results in death;
- Is life-threatening;
- Requires inpatient hospitalization or prolongation of hospitalization (see below for circumstances that do not constitute AEs);
- Results in persistent or significant disability/incapacity (substantial disruption of the ability to conduct normal life functions);
- Results in congenital anomaly/birth defect.

Progression of the malignancy under study (including signs and symptoms of progression) should not be reported as a SAE unless the outcome is fatal within the safety reporting period. Hospitalization due to signs and symptoms of disease progression should not be reported as a SAE. If the malignancy has a fatal outcome during the study or within the safety reporting period, then the event leading to death must be recorded as an AE and as a SAE with severity Grade 5.

Medical and scientific judgment is exercised in determining whether an event is an important medical event. An important medical event may not be immediately life-threatening and/or result in death or hospitalization. However, if it is determined that the event may jeopardize the patient or may require intervention to prevent one of the other outcomes listed in the definition above, the important medical event should be reported as serious.

Examples of such events are intensive treatment in an emergency room or at home for allergic bronchospasm; blood dyscrasias or convulsions that do not result in hospitalization; or development of drug dependency or drug abuse.

Additionally, any suspected transmission via a Pfizer product of an infectious agent, pathogenic or non-pathogenic, is considered serious. The event may be suspected from

PFIZER CONFIDENTIAL

clinical symptoms or laboratory findings indicating an infection in a patient exposed to a Pfizer product. The terms “suspected transmission” and “transmission” are considered synonymous. These cases are considered unexpected and handled as serious expedited cases by pharmacovigilance (PV) personnel. Such cases are also considered for reporting as product defects, if appropriate.

Hospitalization

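### The all-cause Adverse Events and Serious summaries mix neuroblastoma deaths with toxicity, and the plan is inconsistent on whether stand-alone lack-of-efficacy reports are counted

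*Combined protocol and SAP*

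**What the plan says.** Section 8.7.4 sets the scope of the safety tables: "All adverse events collected on the DCT will be listed and summarized for all data reporting milestones". It plans four rows for patients with at least one event (all AEs, treatment-related, serious, serious treatment-related), an AE table and an SAE table by SOC and PT, a full AE listing and an SAE listing. It has no rule for disease progression or lack of efficacy, and the SOC/PT tables are not split by relatedness.

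Section 10 determines what reaches those tables.

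- **Fatal malignancy:** "then the event leading to death must be recorded as an AE and as a SAE with severity Grade 5".
- **Non-fatal progression:** it "should not be reported as a SAE unless the outcome is fatal within the safety reporting period". In addition, "Hospitalization due to signs and symptoms of disease progression should not be reported as a SAE".
- **Lack of efficacy, definition:** "Lack of efficacy" is one of the listed examples of an AE.
- **Lack of efficacy, recording:** the requirements table places it in an exposure-scenario row, apart from the SAE and non-serious AE rows. The entry for recording on the data collection tool (DCT) is "All (regardless of whether associated with an AE), except occupational exposure".
- **Causality:** relatedness is the HCP's judgement of whether there is a reasonable possibility that lorlatinib caused or contributed to the event.

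**The concern.** This is an uncontrolled cohort with relapsed or refractory disease in view. Without a comparator, a reader cannot subtract the background rate of disease events, so the absolute percentages are the safety result. If deaths from neuroblastoma are counted in the Serious row, that row partly repeats what overall survival and PFS already report.

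The protocol recognizes the distinction elsewhere. Section 10 keeps non-fatal progression out of SAEs, and Section 8.7.3 lists progression, adverse event excluding death, and death as separate reasons for discontinuation. Section 8.7.4 does not carry the distinction into the AE tables. Section 8.3 collects date of death but lists no cause of death, so the SAE outputs are the main place where toxic and disease deaths could be told apart. Section 11 foresees use of the results with regulators and in publications.

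**Working it through.** The plan states no expected AE or SAE percentage, so there is no figure to reproduce. The check traces each event type to the tables and then illustrates the size.

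**Step 1. Which rows are affected (Section 10 read with Section 8.7.4)**

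| Event | Adverse Events row | Serious row | Treatment-related rows |
|---|---|---|---|
| Neuroblastoma death in the window | Yes, by rule | Yes, by rule | Only if the HCP judges it related |
| Non-fatal progression, or hospitalization for it | Not stated | No, excluded | Not stated for the non-serious row; not in the serious row |
| Lack-of-efficacy report without an AE | Inconsistent: AE by definition, separate scenario in the requirements table | No rule makes it serious | Only if counted and judged related |

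**Step 2. The window for disease deaths**

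One sentence confines SAE reporting of progression to an outcome fatal within the safety reporting period. The other reads: "If the malignancy has a fatal outcome during the study or within the safety reporting period, then the event leading to death must be recorded". Section 10 runs the reporting period to the end of observation, which must include at least 28 days after the last dose. The 28 days are a minimum, so the two windows largely coincide. The wording should be aligned, but this is a minor matter.

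**Step 3. Size in the Serious row**

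Inputs: N = 50 (the ceiling in Section 8.1); toxicity-only SAE rate s, assumed 20%; share d of patients with a disease-death SAE in the window, assumed 5% to 40%. Under independence, the share with at least one SAE is 1 − (1 − s)(1 − d).

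- d = 5%: 1 − 0.80 × 0.95 = 24% (12 of 50, against 10 from toxicity alone)
- d = 10%: 1 − 0.80 × 0.90 = 28% (14)
- d = 20%: 1 − 0.80 × 0.80 = 36% (18)
- d = 40%: 1 − 0.80 × 0.60 = 52% (26)

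Over the same range of d, s = 10% gives 14.5% to 46%, and s = 40% gives 43% to 64%. Without independence, the row lies between max(s, d) and s + d. For s = 20% this is 20% to 25% at d = 5%, and 40% to 60% at d = 40%.

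**Step 4. Is that range of d plausible?**

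Section 6 cites a median OS of 16.1 months from trials of other treatments. With an assumed exponential curve, the share dead by month t is 1 − 0.5^(t/16.1): 4.2% at 1 month, 12.1% at 3, 22.8% at 6 and 40.3% at 12. These figures only show that the range is not extreme. They do not predict d, because only disease deaths captured in the window count.

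**Step 5. Size in the Adverse Events row**

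As a deliberate upper bound, suppose every progression were filed as lack of efficacy and counted. Section 6 reports that "progression occurred in 54% of patients with refractory disease versus 87% of patients with relapsed disease", again on other treatments. The same formula gives:

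- toxicity-only AE rate 50% (assumed): 1 − 0.50 × 0.46 = 77% to 1 − 0.50 × 0.13 = 93.5%
- toxicity-only AE rate 90% (assumed): 1 − 0.10 × 0.46 = 95.4% to 1 − 0.10 × 0.13 = 98.7%

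If nearly all children have some other AE, this row barely moves. The Serious row matters more.

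**The case against.** The strongest defence is that all-cause AE tables include disease events by design. Section 10 defines an AE without requiring causality, and Section 8.7.4 already gives two treatment-related rows, SOC/PT tables and full listings. A death coded to a progression term would appear under its own PT. The study is descriptive and tests nothing. All of this stands, and it limits the point to interpretability: no planned number is miscalculated. It does not remove the point, because the treatment-related rows give no term-level profile and the listings leave the reader to recompute the percentages.

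Several stronger readings are tempting, and the documents do not support them.

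- A reader might infer that any child whose tumor progresses enters the Serious row. Section 10 excludes non-fatal progression and hospitalization for it.
- A reader might infer that every lack-of-efficacy report is counted as an AE. The requirements table sets it apart from AEs, although the definition includes it. Section 8.4 summarizes AEs after reconciliation with the drug safety unit, which also receives these reports, and that does not settle the matter.
- A reader might infer that lack of efficacy is treatment-related by its nature, so that all four rows are affected. Relatedness is the HCP's judgement.
- A reader might apply the survival and progression figures of Section 6 to this cohort. They come from other treatments. Section 8.2 also ends data collection at discontinuation of lorlatinib, so later deaths may not be captured.

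**Conclusion.** The point holds for the all-cause Adverse Events and Serious rows and for the AE and SAE SOC/PT tables. Neuroblastoma deaths in the window enter them by explicit rule. Whether stand-alone lack-of-efficacy reports enter the AE tables is inconsistent within Section 10. The treatment-related rows are affected only where the HCP judges the event related.

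The size is unknown in advance. The rise in the Serious row from 20% to between 24% and 52% rests on an assumed toxicity rate, an assumed share of disease deaths in the window, and independence. The effect on the any-AE row is small if other AEs are nearly universal. This is a worthwhile, inexpensive improvement to a descriptive plan.

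**What to change.** Amend Section 8.7.4 as follows.

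1. Keep the all-inclusive tables as planned.
2. Add a column to the four AE categories and to the AE and SAE SOC/PT tables that excludes a list of MedDRA terms for neuroblastoma progression and lack of efficacy. Fix the list before the data are summarized, so that exclusions are not chosen on sight of the results.
3. Summarize the excluded terms, fatal and non-fatal, in a table of their own.
4. State that lack-of-efficacy reports without an associated AE are tabulated there, and reconcile the AE definition in Section 10 with its requirements table.
5. Align the two Section 10 sentences on the window for disease deaths.

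One limit should be stated with the list. Section 10 asks for the event leading to death, so a disease death recorded under another term would not be removed by a list of terms alone.

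The cost is some plan wording, a short term list, one added column and one added table. No new data are needed. The downside is slightly longer safety tables.

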8.3. Variables

Variables will include demographics at the start of lorlatinib treatment (age, gender, race, body surface area (BSA)), clinical characteristics (date of initial diagnosis, high risk at diagnosis, ALK aberration date of sample collection and testing, testing platform, ALK and other genetic mutations, ALK amplification, translocation or over-expression, and MYCN amplification, prior anti-cancer treatment, ALK inhibitor use, disease status), treatment start date, starting dose, resupply date(s), BSA, response assessment (date, disease status, HCP reported response, International Neuroblastoma Response Criteria (INRC) response assessment criteria²⁸ and assessment modality), last date of lorlatinib, patient alive, date of death, date of discontinuation of lorlatinib and reason for discontinuation of lorlatinib. Safety data will be collected in DCT as outlined in [Section 10](#).

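### No planned adverse-event summary table uses severity grade, and the plan neither requires a grade for each event nor names a grading scale

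*Combined protocol and SAP*

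**What the plan says.** Section 8.7.4 sets out the safety output. For the overview table, "The number and percentage of patients reporting at least one Adverse Event will be summarized within the following categories": any AE, treatment-related, serious, and serious treatment-related. Two tables by MedDRA system organ class (SOC) and preferred term (PT) follow, one for all AEs and one described as "Serious Adverse Events by SOC and PT". For a patient with several events, "the patient will be counted once for each SOC and once for each PT". The same section adds listings: "All Adverse Event data captured will be listed", with a separate listing of SAEs. Discontinuations for safety reasons go into the disposition summaries and listings.

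On collection, Section 8.3 names no severity variable and defers: "Safety data will be collected in DCT as outlined in" Section 10. There, the HCP must obtain, for each AE, "information adequate both to determine the outcome of the AE and to assess whether it meets the criteria for classification as a SAE", and must also record causality. A grade appears once in the documents, in the Section 10 text on serious adverse events. If the malignancy is fatal during the study or the safety reporting period, "then the event leading to death must be recorded as an AE and as a SAE with severity Grade 5".

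**The concern.** Collection of safety data is the fourth objective in Section 7, and Section 11 intends the report to inform regulatory authorities. A reader of a safety report on children treated under expanded access will want to know how many had severe toxicity attributed to lorlatinib. Seriousness and severity are different attributes. Section 10 defines seriousness by consequence (death, threat to life, hospitalization, disability, birth defect) plus a judgement of medical importance. Severity is the intensity of the event. A set of tables built on seriousness and causality alone leaves intensity out of the summary results. The single mention of Grade 5 suggests that a graded scale was in mind, but the plan does not define it or use it in any summary.

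**Working it through.** There is no figure in the plan to reproduce. The check is a comparison of the planned outputs, the required data and the definition of seriousness.

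1. **Planned summaries (Section 8.7.4).** Overview rows using severity: 0 of 4. SOC/PT tables using severity: 0 of 2. The rule for repeated events counts a patient once per SOC and once per PT, with no instruction to keep the worst grade. Treatment-related AEs have an overview row but no SOC/PT table.

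2. **Required data (Sections 8.3 and 10).** Three assessments are required for each AE: outcome, seriousness and causality. Severity is not among them, and no scale or version is named. Grade 5 is prescribed for one situation only, a fatal malignancy; Grades 1 to 4 are not mentioned.

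3. **Can the serious rows stand in for severity?** Only in part, and they err in both directions.
   - Section 10 gives blood dyscrasias and convulsions without hospitalization as examples of important medical events to be reported as serious. Some severe outpatient events therefore do reach the serious rows.
   - A high-grade event that meets no listed criterion and is not judged medically important stays non-serious. In the overview table it is counted with mild events.
   - A fatal malignancy in the reporting period must be recorded as an SAE, so the serious row also contains deaths from disease.
   - Hospitalization makes an event serious whatever its intensity, so a serious treatment-related event is not necessarily high grade.

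4. **Other outputs.** The disposition summary counts AEs that ended treatment, not severe events managed while treatment continued. Section 8.3 lists starting dose and resupply dates but no dose reduction or interruption, so that indirect sign is not available either. A listing would show grade patient by patient if the DCT captures it, but no count is planned from it.

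5. **Illustration, with assumed counts.** Take the maximum of 50 patients in Section 8.1 and suppose that 45 have any AE. The row prints 45/50 = 90%. It prints the same 90% if 5 patients (5/50 = 10%) or 40 patients (40/50 = 80%) had an event of Grade 3 or higher. The serious rows would tell these two cases apart only to the extent that the high-grade events also met the seriousness definition. The documents give no expected AE rate, so these counts show the mechanism and are not a forecast.

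**The case against.** The strongest reply is that the plan conveys more about severity than its four rows suggest. Section 10 makes certain severe outpatient events serious by example. It also filters laboratory findings: an abnormal result counts as an AE only if it brings symptoms, further testing or intervention, a change in dosing or therapy, or a judgement that it is an AE. Discontinuations due to AEs are reported, the SOC/PT tables name the type of event, and with at most 50 patients full listings are a usable output. All of this stands, and it narrows the gap.

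Three stronger readings are tempting, and the documents do not support them.
- A reader might infer that the safety results as a whole cannot distinguish mild from severe toxicity. That holds for the summary tables only. If the DCT holds a grade, the listings will show it.
- A reader might infer that the DCT has no severity field. The DCT is not in the documents; Section 8 says that it is to be developed. The Grade 5 instruction suggests that a grade can be entered somewhere. What can be said is that the plan does not require a grade for each AE.
- A reader might infer that any severe outpatient toxicity is counted just like a trivial event. The blood dyscrasia and convulsion examples contradict that.

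It can also be said that the objective is to collect safety data, that the analysis is descriptive, that the DCT is deliberately short, and that charts of patients already treated may lack grades. These are reasons to keep the remedy small. They do not supply the missing count.

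**Conclusion.** The point holds for the summary tables. Followed as written, Section 8.7.4 yields no count of patients with high-grade treatment-related events: 0 of 4 overview rows and 0 of 2 SOC/PT tables carry grade, and Sections 8.3 and 10 do not require one for each AE. Seriousness, listings and discontinuations give partial information.

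The size of the loss cannot be stated in patients, because it depends on how many high-grade events turn out to be non-serious, and the documents offer no figure for that. The conclusion rests on the text of the plan; it assumes nothing about what the DCT contains. No effectiveness estimate, sample size or error rate is affected. This is a worthwhile and inexpensive improvement to the reporting of objective 4; it is not a defect that undermines the data collection.

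**What to change.** - **Collection.** Confirm in Section 8.3 or Section 10 that the DCT records a severity grade for each AE, on one named scale and version under which the Grade 5 instruction makes sense. Add the field if it is absent.
- **Overview table in Section 8.7.4.** Add two rows: Grade 3 or higher, and treatment-related Grade 3 or higher.
- **SOC/PT table.** Present it by each patient's maximum grade within SOC and PT, and extend the rule for repeated events accordingly.
- **Missing grades.** Show grade not available as its own column. This agrees with Section 8.7.8, which imputes nothing except partial dates and reports the amount of missing data.

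The cost is at most one DCT field, two rows, a table by maximum grade and a paragraph of text. If the DCT already holds a grade, only the text and the tables change. The drawback is that some events abstracted retrospectively will have no grade, so the Grade 3 or higher counts should be read as minimum counts next to the number ungraded.
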